4.2.8. PFLEX: Pipeline[™] Flex Embolization Device with Shield Technology[™] Clinical Study

The primary objective of the Pipeline[™] Flex Embolization Device with Shield Technology[™] Clinical Study or PFLEX Study was to assess the outcomes of the Pipeline[™] Shield device in patients undergoing treatment for intracranial aneurysms in a real-world, post-market clinical setting. The PFLEX study was conducted in 7 European Union study centers which prospectively consented 58 subjects and attempted to treat a total of 50 target aneurysms in 50 subjects. Ninety-four percent (47/50) of target aneurysms were located in the intracranial ICA (C2 to C7 including the terminus), and 6.0% (3/50) of aneurysms were located in the vertebral artery. Most target aneurysms (48.0%, 24/50) were small (<7 mm), 30.0% (15/50) were medium (7- <13 mm), 20.0% (10/50) were large (13- <25 mm), and 2.0% (1/50) were giant aneurysms (≥25mm). Most subjects (88.0%, 44/50) had unruptured target aneurysms at the time of entry into the study, and 6 (12.0%, 6/50) subjects had previously ruptured aneurysms acutely (<30 days from the study). Device deployment success on a subject level was observed in 100.0% (50/50) of subjects.

In the PFLEX Study, subject follow-up rates were high, with 6-month clinical follow-up data available for 98.0% (49/50) and 1-year clinical follow-up data available for 98.0% (49/50) of subjects for analysis of safety endpoints. Complete aneurysm occlusion without significant parent artery stenosis (\leq 50%) or retreatment of the target aneurysm 1-year post-procedure (primary effectiveness endpoint) occurred in 73.62% of subjects. A total of 78.7% (37/47) subjects had complete occlusion of their target aneurysms and none (0%) had aneurysm recurrence or retreatment through the 1-year follow-up; residual neck was seen in 4.3% (2/47) of subjects, and residual aneurysm was seen in 17.0% (8/47) of subjects. Through 1-year follow-up, majority of subjects (95.7%, 45/47) did not have significant parent artery stenosis, defined as >50% stenosis of the parent artery.

Occurrence of major stroke in the territory supplied by the treated artery or neurological death at 1-year post-procedure (primary safety endpoint) occurred in 0.0% of subjects. There were no major strokes in the territory supplied by the treated artery or neurological death at 30 days post-procedure due to procedural complications. There was no delayed intracerebral hemorrhage >30 days through 1-year post-procedure (0.0%; 0/50). The overall mortality rate was 0.0% (0/50). Summary of primary endpoints of PFLEX study is presented in **Table 4-2**.

Endpoints	Rates	1-Sided
		97.5% Exact
		Binomial
		Confidence
		Interval
Primary Effectiveness Endpoint: Complete aneurysm occlusion (defined as Raymond-Roy g	ra de 1 ¹) without	significant
parent artery stenosis (≤ 50%) or retreatment of the target a neurys mat 1-year post-proced	lure	
ITT‡ population (N=50)	73.62%	59.39%*
ICA# Population (N=47)	74.23%	59.24%*

Table 4-2. Summary of Primary Endpoints of PFLEX Study

Medtronic Controlled Information

PR-1	VV16	099
------	------	-----

Version C

Page 43 of 144

Primary Safety Endpoint: Occurrence of major stroke in the te	rritory supplied by the treated artery or ne	urological death a
1-year post-procedure		
ITT‡ population (N=50)	0.0%	7.1%†
ICA# population (N=47)	0.0%	7.5%†
*Lower Bound of the Binomial Confidence Interval		
[†] Upper Bound of the Binomial Confidence Interval		
‡Intention to Treat (ITT) population included all consented subjects in w	'hom deployment of the Pipeline™ Shield device	was attempted.
#Internal Carotid Artery Population (ICA Population) is defined as a subs	set of ITT population that included only those sub	jects in whom the
Pipeline [™] Shield device was implanted in the ICA (segments C2-C7 incl	uding the terminus).	

Overall, a high rate of complete aneurysm occlusion was achieved with the use of the Pipeline[™] Shield device in the treatment of intracranial aneurysms. The incidence of major stroke, neurological death, and delayed intracerebral hemorrhage in the PFLEX study were low. Therefore, results from the PFLEX Study demonstrated that the Pipeline[™] Shield device is effective and safe for the endovascular treatment of intracranial aneurysms.

4.3. Purpose

A Study of the Pipeline[™] Vantage Embolization Device with Shield Technology[™] for Endovascular Treatment of Wide-Necked Intracranial Aneurysms (ADVANCE Study) is a prospective, global, multicenter, single-arm IDE study of the Pipeline[™] Vantage device for the treatment of adults (22 years of age or older) with wide-necked intracranial aneurysms located in the internal carotid artery (ICA) (up to the terminus). The primary purpose of the ADVANCE Study is to assess the safety and effectiveness of the Pipeline[™] Vantage device in the treatment of unruptured intracranial aneurysms within the intended indication for use. The safety of the Pipeline[™] Vantage will be assessed through incidence of major stroke in the territory supplied by the treated artery or neurological death at 1-year post-procedure. The effectiveness of the Pipeline[™] Vantage will be assessed through incidence of complete aneurysm occlusion (Raymond Roy Scale Class 1) without significant parent artery stenosis (\leq 50%) or retreatment of the target aneurysm at 1-year post-procedure. Additional safety and effectiveness analyses will include incidence of major stroke in the territory supplied by the treated artery or neurological death at 2- and 3years post-procedure, incidence of major stroke in the territory supplied by the treated artery or neurological death at 30 days post-procedure, incidence of delayed intraparenchymal hemorrhage >30 days post-procedure through 1-year post-procedure, incidence of subjects with disabling strokes that have a mRS decline to a score of 3 or more (mRS \geq 3) due to a stroke-related cause assessed at a minimum of 90 days post-stroke event at 1 year, 2 year, and 3 year post-procedure, incidence of successful device implantation at the target site, incidence of complete aneurysm occlusion (Raymond Roy Class 1) at 1and 3-years post-procedure, incidence of target aneurysm recurrence at 1- and 3-years post-procedure.

PR-NV16099

5. Objectives and Endpoints

5.1. Objectives

5.1.1. Primary Objective(s)

The primary objective of this study is to assess the safety and effectiveness of the Pipeline[™] Vantage Device in the treatment of intracranial aneurysms within the intended indication for use*.

*The Pipeline[™] Vantage Embolization Device with Shield Technology[™] is intended for endovascular treatment of adults (22 years of age or older) with wide-necked intracranial aneurysms located in the internal carotid artery (up to the terminus).

5.1.1.1. Primary Endpoints

5.1.1.1.1. Primary Effectiveness Endpoint

The following will be assessed for the primary effectiveness endpoint:

 \circ Incidence of complete aneurysm occlusion (Raymond Roy Scale Class 1) without significant parent artery stenosis (≤ 50%) or retreatment of the target aneurysm at 1-year post-procedure.

Complete occlusion and parent artery stenosis will be adjudicated by the Imaging Core Laboratory. Retreatment will be assessed per site records.

5.1.1.1.2. Primary Safety Endpoint

The following will be assessed for the primary safety endpoint:

• Incidence of major stroke in the territory supplied by the treated artery or neurological death at 1year post-procedure

This endpoint will be adjudicated by the independent Clinical Events Committee (CEC).

For the purposes of this study protocol, stroke is defined as a focal neurological deficit of presumed vascular origin persisting ≥24 hours from symptom onset and a neuro-imaging study or other quantitative study that does not indicate a different etiology. The 24-hour criterion is excluded if the subject undergoes cerebrovascular surgery or dies during the first 24 hours.

The definition includes:

- Subjects presenting with clinical signs and symptoms suggestive of SAH, intracerebral hemorrhage, or cerebral infarction.
- Sudden loss or worsening of visual acuity due to retinal artery occlusion or retinal emboli.

PR-NV16099

The definition excludes:

- Slowly progressive cranial nerve palsies or progressive visual field deficits due to continued aneurysm growth.
- Stroke events in cases of blood disorder such as leukemia or external events such as trauma.

Severity of stroke will be classified by the CEC as major or minor:

- Major Stroke: A stroke, which is present for \geq 24 hours and increases the NIHSS of the subject by \geq 4.
- Minor Stroke: A stroke, which is present for ≥ 24 hours and increases the NIHSS of the subject by ≤ 3 .

Disability status of the Stroke events will be assessed based on mRS assessment conducted at a minimum of 90 days post stroke event:

- Disabling: (mRS with poor functional outcome i.e. ≥3 points)
- Non-Disabling (mRS with good functional outcome 0-2 points)

The following assessments are required to be performed (if hospitalized at the primary investigative site) or source documents obtained (if hospitalized at an outside hospital) for All Stroke Events:

- o NIHSS at time of Stroke presentation to the hospital
- NIHSS at 24 hrs from the Stroke presentation
- o mRS assessment at a minimum of 90 days post-Stroke event
- Any Imaging / imaging report available during Stroke hospitalization

Neurological death is any death of a subject in which the primary cause of death is due to neurologic reasons.

The following documents are to be obtained for all events that lead to Death:

- Hospitalization Record (where available)
- Autopsy Report (where available)
- Death Certificate (where available)

A PI note describing the last subject contact with detail of any assessments to be provided where Death Certificate is not available.

PR-NV16099

5.1.2. Secondary Objective(s)

The secondary objective of this study is to assess the efficacy and safety of the Pipeline[™] Vantage Device in the treatment of intracranial aneurysms within the intended indication for use.

5.1.2.1. Secondary Endpoint(s)

The following will be assessed for the effectiveness outcome measures:

- 1. Incidence of successful device implantation at the target site
- 2. Incidence of complete aneurysm occlusion (Raymond Roy Class 1) at 1- and 3-years postprocedure
- 3. Incidence of target aneurysm recurrence at 1- and 3-years post-procedure

For the purposes of this study protocol, successful device implantation will be presented in terms of Procedural Technical Success and Device Technical Success. Procedure technical success is measured by the rate of successful implantation of the study device during the study index procedure at the target site regardless of the number of devices deployed and implanted at the target site. Device technical success is measured by the rate of successful study device implantation at the target site with the total number of devices attempted to be deployed.

Successful device implantation and retreatment will be site reported. Aneurysm occlusion class, recurrence, and parent artery stenosis will be assessed by the independent Imaging Core Lab.

The following will be assessed for the secondary safety endpoints:

- 1. Incidence of major stroke in the territory supplied by the treated artery or neurological death at 2- and 3-years post-procedure
- 2. Incidence of major stroke in the territory supplied by the treated artery or neurological death at 30 days post-procedure
- Incidence of delayed intraparenchymal hemorrhage >30 days post-procedure through 1-year post-procedure
- Incidence of subjects with disabling strokes that have a mRS decline to a score of 3 or more (mRS ≥ 3) due to a stroke-related cause assessed at a minimum of 90 days post-stroke event at 1 year, 2 year, and 3 year post-procedure

The events comprising the safety endpoints will be adjudicated by the independent CEC.

PR-NV16099

Version C

Page 47 of 144

6. Study Design

The study is a prospective, global, multi-center, single-arm IDE clinical study evaluating the performance of the Pipeline[™] Vantage Device. The Pipeline[™] Vantage Device is investigational in the United States and Canada.

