9.8. Retreatment

At the Investigator's discretion, the target aneurysm may be retreated at any time during the study. The retreatment procedure can include any endovascular or surgical intervention including the implant of the Pipeline[™] Vantage Device. In such situations, the date that the subject receives the initial Pipeline[™] Vantage Device implant (and not the date of the retreatment) will be considered Day 0.

Reason(s) for retreatment of aneurysm shall be documented:

- Device Movement
 - Foreshortening (Peri-procedural or Delayed)
 - Migration
- Aneurysm Growth
- Aneurysm Rupture
- Aneurysm Non-Occlusion
- Insufficient Neck Coverage

Type of Retreatment will be documented:

- Planned
- Unplanned

A retreatment will be considered an "Unscheduled Visit" and subjects will be required to undergo the following study assessments:

- Full neurological exam and assessment of aneurysm symptoms (new, worsened, improved, stable)
- Record concomitant and protocol-specified medications
- Imaging (per standard of care)
- NIHSS
- mRS assessment to be carried out by a certified independent assessor at site
- Assessment of Adverse events

		· · · · · · · · · · · · · · · · · · ·	and the second sec
PR-NV16099	Version C	Page 83 of 144	Medtronic

Data will be collected for all retreatment procedures in the Retreatment eCRFs. Retreatments should be reported as an SAE.

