12.2.3. Aneurysm Occlusion

Post-procedure and follow-up angiograms will be reviewed to assess an urysm occlusion according to the Raymond Roy Scale¹ (**Figure 12-1**).

[figure not shown]

Figure 12-1. Raymond Roy Scale for Grading Aneurysm Occlusion

- **Class 1: Complete Occlusion** = Complete obliteration of the aneurysm
- **Class 2: Residual Neck** = Persistence of any portion of the original defect of the arterial wall as seen on any singe projection, but without opacification of the aneurysmal sac
- Class 3: Residual Aneurysm = Any opacification of the aneurysmal sac

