13.8.3. Secondary Endpoint Analysis

All the secondary endpoints will be summarized using frequency tables presenting counts and percentages; no statistical testing will be performed against any preset thresholds for the secondary endpoints. The secondary endpoints include the following:

The following will be assessed for the effectiveness outcome measures:

- 1. Incidence of successful device implantation at the target site
- 2. Incidence of complete aneurysm occlusion (Raymond Roy Class 1) at 1- and 3-years postprocedure
- 3. Incidence of target aneurysm recurrence at 1- and 3-years post-procedure

The following will be assessed for the secondary safety endpoints:

- Incidence of major stroke in the territory supplied by the treated artery or neurological death at 2- and 3-years post-procedure
- 2. Incidence of major stroke in the territory supplied by the treated artery or neurological death at 30 days post-procedure
- Incidence of delayed intraparenchymal hemorrhage >30 days post-procedure through 1-year post-procedure

ADVANCE Clinical Investigation Plan			
PR-NV16099	Version C	Page 114 of 144	Medtronic

Incidence of subjects with disabling strokes that have a mRS decline to a score of 3 or more (mRS ≥ 3) due to a stroke-related cause assessed at a minimum of 90 days post-stroke event at 1 year, 2 year, and 3 year post-procedure

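### The 3-year complete-occlusion endpoint has no retreatment condition, so an aneurysm that was retreated and then closed counts as a device occlusion

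*Combined protocol and SAP*

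**What the plan says.** - **Secondary endpoint.** Section 5.1.2.1 lists "Incidence of complete aneurysm occlusion (Raymond Roy Class 1) at 1- and 3-years postprocedure". The Synopsis and Sections 4.3 and 13.8.3 agree, and none adds a retreatment condition.
- **Grading.** Class 1 is purely anatomical. Section 12.2.3 defines it as "Complete obliteration of the aneurysm", whatever treatment achieved it.
- **Retreatment.** Section 9.8 leaves the decision to the investigator and sets no time limit: "the target aneurysm may be retreated at any time during the study". The choice of method is equally open, since Section 9.8 adds: "The retreatment procedure can include any endovascular or surgical intervention". Among the listed reasons is "Aneurysm Non-Occlusion". The initial implant date stays Day 0.
- **Primary endpoint.** Section 5.1.1.1.1 requires Class 1 without stenosis above 50% "or retreatment of the target aneurysm at 1-year post-procedure". Retreatment is therefore a failure, but only up to 1 year.
- **Analysis.** Section 13.8.3 says "All the secondary endpoints will be summarized using frequency tables presenting counts and percentages", with no test against a threshold.
- **Populations and missing data.** Section 13.3 keeps retreated subjects in the ITT population. The per-protocol exclusions concern the index procedure and baseline mRS, not later retreatment. Section 13.4 has no rule for retreated subjects.

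**The concern.** The protocol's case for flow diversion rests on durability. Section 6.2 criticises stent-assisted coiling for failing to sustain occlusion and for the retreatment that follows. The 3-year occlusion rate is the trial's main evidence on that question. As defined, it mixes aneurysms closed by the study device with aneurysms closed by a later coil, clip or further implant.

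The situation is foreseeable. Sections 9.9.4 and 9.9.5 require DSA at 2 and 3 years when the aneurysm is not occluded, so persistent filling will be seen and may lead to retreatment. Section 4.2.2 reports that complete occlusion in PUFs rose from 86.8% at 1 year to 95.2% at five years. If this trial shows a similar late rise, the endpoint as worded cannot separate progressive closure by the device from rescue by another treatment.

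**Working it through.** **1. The plan's own figures.** No target, power or expected rate is stated for the secondary occlusion endpoint. The nearest stated figures are the primary-endpoint powers in Section 13.2. An exact one-sided binomial test against 50% at 2.5% gives:

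| n | Reject at | True rate | Power computed | Power stated |
|---|---|---|---|---|
| 100 | ≥61 successes | 65% | 82.76% | 82.8% |
| 80 | ≥50 successes | 67% | 83.54% | 83.5% |

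Both reproduce. Neither depends on how the secondary endpoint is scored.

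**2. Following one aneurysm through the definitions.** Suppose it still fills on the 1-year DSA, is coiled or clipped at month 14, and is Class 1 at 3 years.
- Primary endpoint: failure at 1 year, which is correct.
- 3-year occlusion: success, because only the anatomy is graded and Day 0 has not moved.
- 3-year recurrence: not an event, because the Glossary requires earlier complete occlusion.

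No effectiveness endpoint after 1 year registers the retreatment.

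**3. Bound on the overstatement.** Let N be the subjects imaged at 3 years, R those retreated earlier, and S those retreated who are Class 1.

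Overstatement = S/N ≤ R/N, because S ≤ R.

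It is never negative: with the same denominator, the as-observed count includes every subject in the retreatment-free count.

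**4. Bound applied to the cited Pipeline studies (1-year data, Sections 4.2.5, 4.2.7 and 4.2.8).** The worst case is that every retreated aneurysm was Class 1 and in the denominator.

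| Study | Complete occlusion | Retreated | If all retreated are removed | Difference |
|---|---|---|---|---|
| PREMIER | 113/138 = 81.9% | 4/139 = 2.9% | 109/138 = 79.0% | 2.9 points |
| SHIELD | 141/188 = 75.0% | 4/200 = 2.0% | 137/188 = 72.9% | 2.1 points |
| PFLEX | 37/47 = 78.7% | 0 | 37/47 = 78.7% | 0 |

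The SHIELD sentence is broken in the available text; 4/200 is read here as its retreatment count.

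**5. Bound in this trial.** The documents give no 3-year retreatment rate, so the rate is an assumption. With 80 to 100 imaged subjects:

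| Assumed retreatment by 3 years | Subjects | Maximum overstatement |
|---|---|---|
| 2% | 1.6 to 2 | 2 points |
| 2.9% | 2.3 to 2.9 | 2.9 points |
| 5% | 4 to 5 | 5 points |
| 10% | 8 to 10 | 10 points |

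The 10% row borrows the upper figure in Section 6.2 for stent-assisted coiling of small and medium aneurysms. It is not a Pipeline rate.

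**The case against.** The best defence is that little turns on this and nothing is hidden. The endpoint is descriptive. Every retreatment is reported as an SAE on its own eCRF, with a reason and a planned or unplanned label (Section 9.8). It is an event of interest (Section 10.1) that the CEC adjudicates (Section 12.1). Section 13.1 promises a detailed SAP that could hold a scoring rule. The protocol also reports earlier studies' plain occlusion rates separately from retreatment, so the as-observed rate has comparative value.

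Most of that stands, and it limits the severity. It does not close the gap. Section 13.8.3 commits to no scoring rule, and the tables in Section 13.8.4 are organised by relatedness, seriousness and severity, with no retreatment rate. In a single-arm trial the rule is best fixed before the data are seen.

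Three stronger readings are tempting, and the documents do not support them.
- **The 1-year result is also compromised.** It is not: the primary endpoint already scores retreatment as failure at 1 year, and the secondary 1-year rate is its anatomical component.
- **A reopened and retreated aneurysm escapes the recurrence endpoint.** The Glossary defines recurrence as complete occlusion followed by Class 2 or 3 at a follow-up exam. A reopening seen by the core lab on imaging before the retreatment can fit that. What is unclear is whether recurrence at 3 years is cumulative.
- **The inflation is large.** One could assume that 25% to 50% of aneurysms open at 1 year are retreated and close, giving (1 − 0.82) × 0.25 = 4.5 points to (1 − 0.75) × 0.50 = 12.5 points. Nothing in the documents supports that fraction. The cited 1-year retreatment rates, set against the share not occluded, give 2.9/18.1 = 16% in PREMIER, 2.0/25.0 = 8% in SHIELD and 0 in PFLEX. PUFs had higher 1-year occlusion (86.8%) and 95.2% at five years, on different denominators. Aneurysms open at 1 year are therefore not simply a pool awaiting rescue.

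**Conclusion.** The point holds for the 3-year complete-occlusion endpoint. As literally defined, it counts a retreated and then closed aneurysm as an occlusion, and no effectiveness endpoint after 1 year corrects for that. The plan is silent on scoring such cases; it does not expressly choose to count them as successes.

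The direction is certain: the reported rate can only rise. The size is at most about 2 to 3 points if retreatment by 3 years stays near the cited Pipeline 1-year rates of 0 to 2.9%, and at most 10 points if the rate quoted for stent-assisted coiling applied. Both are upper bounds that assume every retreated aneurysm is Class 1 at 3 years. Trial success, power and sample size are unaffected. The consequence is confined to how the durability result can be read.

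**What to change.** In Sections 5.1.2.1 and 13.8.3:

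1. At 3 years, report two rows side by side: Class 1 occlusion with no target aneurysm retreatment through that visit, scoring any earlier retreatment as not occluded; and the as-observed Class 1 rate. Keep the protocol's existing definition of retreatment, including the Section 9.5.6 provision that a successful second attempt after a failed deployment is not one.
2. State that recurrence by 3 years is cumulative and includes a reopening confirmed by the core lab on imaging obtained before a retreatment.

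The 1-year secondary rate can stay as it is. No rule on when or how to retreat changes. The cost is one extra table row, two sentences of definition and possibly a slightly less favourable 3-year figure. The retreatment data are already collected.
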